#### 8.1.3. Lung Function

Lung function is evaluated by using a non-invasive spirometer to determine the Slow Vital Capacity (SVC). During the test, the patient inspires fully and then slowly expires all the air in his/her lungs. The test will be done using a facemask. This procedure is repeated 3 times minimally until a steady recording is obtained; the highest score is recorded. A digital spirometer is used to determine SVC values. The SVC will be assessed at Screening, Baseline, and weeks, 12, 24, 36, 48, 60, and 72. The results of SVC in liters will be recorded in the eCRF by the investigator or designee.

#### 8.1.4. Staging of Disease Progression

The King's staging system is a simple clinical staging system, which defines four stages of ALS. The first three stages are defined by functional involvement of a region: bulbar, upper limbs and lower limbs. The number of regions involved gives the stage. Stage 4 is reached if swallowing (4A) or respiratory (4B) difficulty is severe enough to require intervention. MiToS is a similar clinical staging system, in which the stages are defined as loss of independence on the four domains of the ALSFRS-R: swallowing, walking/self-care, communicating and breathing. The investigator will assess both staging systems for each patient and will record the results in the eCRF. The assessments will be performed at Baseline and weeks 12, 24, 36, 48, 60, and 72.

#### 8.1.5. Strength Test

Handheld dynamometry (HHD) is a procedure for quantitative strength testing. This testing will be conducted by the Investigator or any designee who has been properly trained for the quantitative muscle strength evaluation. When possible, it is highly recommended that

---

all assessments be performed by the same assessor. Muscle strength testing will be performed on prespecified muscles in the upper and lower extremities bilaterally and the force measurement recorded. HHD will be assessed at Baseline and weeks 12, 24, 36, 48, 60, and 72. The results of the HHD will be recorded in the eCRF by the investigator or designee.

#### **8.1.6. Health Status**

ALSAQ40: The Amyotrophic Lateral Sclerosis Assessment Questionnaire is a patient reported outcome (PRO) designed to determine the patient's health status. The ALSAQ40 is specifically used to measure the subjective well-being of patients with ALS. There are 40 items/questions in the long form, the ALSAQ40, with 5 discrete scales: physical mobility (10 items), activities of daily living and independence (10 items), eating and drinking (3 items), communication (7 items), emotional reactions (10 items). During the study the questionnaire will be provided in the local language of the patient. The ALSAQ40 questionnaire will be completed by the patient at Baseline and weeks 24, 48, and 72 via a study App or online questionnaire. In case of technical issues with the ePRO device these questionnaires can be completed on a paper version as a backup.

EQ-5D-5L is a patient reported outcome (PRO), simple, valid, standardized health state measure. It consists of five questions that relates to five dimensions of health: mobility, self-care, usual activities, pain/discomfort and anxiety/depression. Each dimension/question can be scored on three levels of severity (1, no; 2, slight; 3, moderate; 4, severe; 5, extreme problems). In addition, responders will be asked to rate their current health related quality of life (HRQoL) on a visual analogue scale (VAS) ranging from 0 (bad) to 100 (very good). During the study the questionnaire will be provided in the local language of the patient. The EQ-5D-5L and VAS will be completed at Baseline and weeks 12, 24, 36, 48, 60 and 72 via a study App or online questionnaire. In case of technical issues with the ePRO device these questionnaires can be completed on a paper version as a backup.

#### **8.1.7. Cognition**

The neuropsychological status of patients will be evaluated using the Edinburgh Cognitive and Behavioral ALS Screen (ECAS). The ECAS is independent of motor disability and evaluates five cognitive domains: language functions, executive functions, letter fluency, memory and visuospatial functioning. The ECAS is designed for ALS patients and answers can be given verbally, or by a combination of writing or pointing. It is suitable for patients who are anarthric or patients who have no hand motor function. The total score is 136 points and should take no longer than 15 minutes to administer. The ECAS will be completed by the investigator or designee at Baseline and weeks 24, 48, and 72. The total score of the questionnaire will be recorded in the eCRF.

### **8.2. Safety Parameters**

Occurrence of AEs, changes on physical examination (including body weight), vital signs, ECG parameters and laboratory examinations (biochemistry, haematology and urinalysis) will be registered throughout the entire study duration.

---

All AEs will be actively collected at each visit, from spontaneous declarations of the patient as well as from oral inquiry and clinical examination. All concomitant medications and/or therapies should be documented in the patient file and reported in the electronic Case Report Form (eCRF).

### **8.2.1. Physical and neurological examination**

Physical examinations will be performed by qualified personnel according to the Schedule of Events. Symptom directed physical exams will be performed as applicable. Physical examination includes the following assessments: general appearance, head, eyes, ears/nose/throat, neck, lymph nodes, skin, lungs, heart, abdomen, musculoskeletal, and neurologic evaluations. Breast, rectal, and genitourinary/pelvic exams should be performed when clinically indicated. Weight (kilograms) will be measured as part of all physical examinations. Height (centimeters) will be measured only at the screening visit. The BMI will be calculated.

Neurological examination will be performed by qualified personnel according to the Schedule of Events to assess possible peripheral nerve dysfunction (= sensory or motor symptoms), diminished or absent reflexes (compared with baseline examination), sensory abnormalities (e.g. numbness or tingling) or weakness. In case a subject experiences clinical signs or symptoms at home, subjects will be asked to contact the clinic.

All abnormal findings will be documented in the database.

### **8.2.2. Laboratory Parameters**

The results of clinical laboratory tests conducted at the screening visit must be assessed by the investigator to determine each subject's eligibility for participation in the study. The results of all clinical laboratory tests conducted during the study must be assessed by the investigator to assess patients' safety.

Any significant abnormalities is to be documented and followed up as AEs and should be fully investigated. Whenever possible, the etiology of the abnormal findings will be documented in the database. Laboratory results with significantly abnormal values should be investigated as such and checked for verification. Additional tests and other evaluations required to establish the significance or etiology of an abnormal result or to monitor the course of an AE should be obtained when clinically indicated. In particular, if a clinically significant abnormal result is observed that is not resolved by the final study visit, repeat tests will be performed if possible and resolution or stability of the abnormality will be recorded in the source documentation.

Any significant laboratory abnormalities that are either serious or unexpected will be promptly reported to the sponsor's Medical Monitor. Any additional relevant laboratory results obtained by the investigator during the course of this study will be reported to the sponsor or its representative.

---

**8.2.3. ECG**

Twelve-lead ECGs will be performed according to the Schedule of Events. Subject should be resting supine/semi-supine for at least 5 minutes prior to all ECG measurements if possible.

**8.2.4. Vital Signs**

Vital signs, including blood pressure, heart rate, respiratory rate, pulse oximetry, and temperature, will be measured at study visits according to the Schedule of Events. Subject should be resting supine/semi-supine for at least 5 minutes prior to vital signs measurements.

**8.2.5. Nerve Conduction Study**

The NCS protocol evaluates the sensory nerve action potential (SNAP) amplitudes using standard ring-electrodes and predefined sites for both stimulus (antidromic) and recording sites, including standardized distances that also apply for the inter-electrode distances. Hence, routine signal averaging for the recorded SNAP's will be performed after supramaximal stimulation. These measures will eliminate any unwanted variation due to instrumental differences. For these recordings, limb temperature should be at 31°C, otherwise warming may be considered or alternatively accepted correction factor for decreased temperature could be done. Sensory latencies and velocities are less robust parameters that may also depend on filter settings between different machines and, therefore, will not be used. NCS criteria for neuropathy are decreased sural nerve SNAP amplitudes or decreased sural/radial nerve amplitude ratio (SRAR).

NCS will include sensory recordings from sural nerves (unilateral) and sensory recordings from median, ulnar, radial nerves (unilateral) with standardized distances between recording and stimulation sites of 12cm. NCS data will be evaluated by neurophysiologists at the participating centres and also reviewed independently at the UMC Utrecht, taking into account reference values provided by participating sites, and using age adjusted reference values. Additional testing may be requested if required.

Instructions on operational aspects of the NCS are described in a separate NCS manual.

The main aim of NCS is to identify subclinical damage of sensory function before the potential development of a clinically significant neuropathy. The relevant expected clinical presentation of neuropathy is predominantly sensory and includes relative symmetric paraesthesia and/or numbness mainly in feet.

The DSMB will assess the results of the NCS, simultaneously with the assessment on vitamin B6, clinical signs, ALSFRS-R questions related to leg functioning (8. walking and 9. climbing stairs) for the first enrolled 60 patients (about 40 active and 20 placebo).

The NCS will be conducted for the first enrolled 60 patients at screening, and on weeks 4, 12, and 24. Then according to the evaluation by the DSMB, one of the following options will be performed:

---

- If no neurological concerns are observed, the study will continue with one additional NCS at week 48 for the first 60 patients. Then for the next enrolled patients, one NCS will be performed at screening and another one at week 48. Additional NCS(s) could be performed between screening and week 48 if any abnormality is detected by the neurological examination or any suggesting symptoms of neuropathy are reported by the patient.
- If NCS show signs of neurological damage, intensive NCS monitoring will continue for all patients at screening and on weeks 4, 12, 24, 36, 48, 60, and 72.

All NCS values will be recorded by the investigator in the eCRF at the corresponding time points.

### **8.3. Pharmacokinetic Assessments**

Details of analyses methods of the pharmacokinetic, population PK, pharmacokinetic-pharmacodynamic modelling and pharmacokinetic interaction between FAB122 and riluzole as well as the software packages used will be described in a separate PK analysis plan that will be finalized before the database closure and the formal treatment code breaking.

The plasma concentration for FAB122 and riluzole will summarized over time. The primary pharmacokinetics parameters of interest derived of the plasma concentration of FAB12 and riluzole are:  $C_{max}$ ,  $T_{max}$ ,  $t_{1/2}$ , and AUC.

Pharmacokinetic parameters may include, but not be limited to (see table 5):

**Table 5: Pharmacokinetic parameters of FAB122 and riluzole**

Parameter	Definition
AUC last	Area under the concentration-time curve from time 0 (time of drug administration) to the time of the last quantifiable concentration; calculated using the linear trapezoidal rule
C max	Maximum plasma concentration
T max	Time of the maximum plasma concentration
C last	Last quantifiable concentration
T last	Time of the last quantifiable concentration
T 1/2	Time taken for C max to drop in half
AUC inf	Area under the concentration-time curve from time 0 to infinite

The pre-dose concentration may be extrapolated to the 24-hour time point to estimate AUCtau, Vss/F and CL/F.

### 8.3.1. Population and profiling PK Analysis

FAB122 plasma concentration-time data will be subjected to a population PK analysis using nonlinear mixed-effects modelling. Blood sampling for FAB122 PK analysis will be done in ~90 subjects. Of those ~30 subjects will participate in a PK profiling sampling schedule at baseline, week 4 and week 48 and a population PK sampling schedule at baseline, ~60 subjects participate in the population PK sampling schedule at baseline, week 4 and week 48. Plasma concentrations of all these PK samples may be included in the population PK analysis. For this analysis, the data may be combined with results of other studies. The aim of the population PK analysis is to develop a compartmental model of the FAB122 concentration vs. time profiles, which will provide a good understanding of the inter-subject and intra-subject (if possible) variability in the exposure. Available subject characteristics (such as demographics, laboratory variables and co-medication) will be tested as potential covariates affecting PK parameters.

It is estimated that about 90% of the patients included in this study will concomitantly receive riluzole treatment. Results from pharmacokinetic profiling and population PK analysis will therefore also be used to study the effect of riluzole on FAB122 concentrations and vice versa. Therefore, mean plasma PK parameters of subjects who received FAB122 and riluzole will be compared to those of subjects who received riluzole and placebo.

In addition, blood sampling for the determination of riluzole concentrations will be done in the subjects included in FAB122 PK sampling in baseline and week 4 (~60 subjects). Mean plasma Ctrough and Cmax levels of subjects who received riluzole and FAB122 at

---

baseline visit and after 4 weeks of treatment with FAB122, as well as changes in these metrics between baseline and week 4 will be compared to those of subjects who received riluzole and placebo. If needed and feasible, modelling will be applied to support statistical analysis methods.

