## 4. STUDY DESIGN

Multicenter, multinational, double-blind, randomized (2:1), placebo-controlled Phase III study to investigate the efficacy and safety of 100 mg FAB122 (former TW001) once daily as oral formulation in ALS patients.

Subjects will be screened to assess whether they comply with all enrolment criteria. Approximately 300 patients will be randomized to 100 mg FAB122 or matched placebo in a 2:1 ratio. Patients will be stratified by;

- 1) their ALS progression rate at the start of the study (the slope ALSFRS-R score from time of first symptoms till Screening <1.0 vs.  $\geq 1.0$ ),
- 2) additional co-medication for ALS (a. riluzole, b. no riluzole).

Riluzole (100 mg/day or less) may be used as background (add-on) therapy. Patients on riluzole should be on stable doses at the start of the trial and for at least 30 days before the initiation of the study drug. It will not be allowed to initiate riluzole therapy during the trial. Additional supportive Standard Of Care (SOC) treatments will be allowed in all patients and will be standardized as much as possible.

Subjects will receive double-blind treatment up to a maximum of 72 weeks. The study is planned to continue until the last randomized subject has reached 48 weeks of follow up (or has reached an intercurrent event) AND the first one third of the subjects randomized (100) have reached 72 weeks of follow up (or has reached an intercurrent event). Subjects who discontinue treatment before week 72 will be followed as much as possible according to the planned visit schedule. In case of sanitary restrictions due to COVID-19 pandemic, home visits might be performed (for more details, see annex 4).

[figure not shown]
Subjects will visit the clinic at Screening, Baseline, Week 4, Week 12, and every 12 weeks thereafter. Monthly telephone visits are performed in between the visits to the clinic until Week 48.

Blood sampling for FAB122 plasma concentrations will be done in ~90 subjects treated with the study drug.

After a subject completed the study (max at 72 weeks), he/she will be offered the possibility to roll over in an open label extension trial in which all subjects will be offered to receive FAB122.

The end of the trial will correspond to the last subject last visit per the trial schedule.

The study flowchart is presented in the Figure 2.

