**Blood Sampling Riluzole**

Blood sampling for the determination of riluzole concentration will be done in the subjects included in FAB122 PK sampling in baseline and week 4 (~90 subjects) at (1) pre-dose (within 1 hour prior to dosing).(2) within 5- and 30-minutes post dosing, (3) 1 hour and (4) 1.5 hour after the second PK sample was taken. The time of sampling will be accurately recorded.

Patient should come fasted and will take the riluzole dose in the clinic, at the same time that the IMP dose.

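### The riluzole interaction comparison named in Section 8.3.1 informs only FAB122's effect on riluzole, and the change in riluzole Cmax starts from a baseline already under FAB122

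*Protocol*

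**What the plan says.** Protocol Section 8.3.1 says that the profiling and population PK results will be used to "study the effect of riluzole on FAB122 concentrations and vice versa". It follows this with a single group comparison: "Therefore, mean plasma PK parameters of subjects who received FAB122 and riluzole will be compared to those of subjects who received riluzole and placebo".

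Other parts of the same section bear on the question:

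- For the population PK model: "Available subject characteristics (such as demographics, laboratory variables and co-medication) will be tested as potential covariates affecting PK parameters". Pooling with other studies is also allowed.
- For riluzole, mean trough and Cmax levels at baseline and after four weeks are compared with the riluzole-plus-placebo group, and the sentence adds: "as well as changes in these metrics between baseline and week 4 will be compared to those of subjects who received riluzole and placebo".
- On background use: "It is estimated that about 90% of the patients included in this study will concomitantly receive riluzole treatment".

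On sampling days the patient, according to Section 6.7, "will take the riluzole dose in the clinic, at the same time that the IMP dose". Section 6.2 places the first FAB122 dose at the baseline visit. Table 3 shows one pre-dose sample at that visit, with all others after the joint dose.

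On numbers, Section 4 says: "Blood sampling for FAB122 plasma concentrations will be done in ~90 subjects treated with the study drug". Riluzole sampling covers about 90 subjects in Section 6.7 but about 60 in Section 8.3.1.

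Section 8.3 leaves the detailed methods, including those for the interaction, to a separate PK analysis plan. SAP Sections 1, 5.6.2 and 5.6.4 likewise place PK analysis outside the SAP.

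**The concern.** Two analysis rules in Section 8.3.1 do not fit their purpose.

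First, a two-way question is followed by a one-way comparison. To see whether riluzole changes FAB122 exposure, one needs FAB122 patients with and without riluzole. Neither the protocol nor the SAP names that comparator.

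Second, a change from baseline measures an effect only if baseline is free of it. Here the baseline riluzole Cmax is measured after FAB122 and riluzole have been taken together. Any part of an interaction that appears within hours is in both visits and drops out of the change.

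At stake is an exploratory objective (Section 3.1.3): whether the single fixed dose gives similar exposure in the roughly 90% of patients on riluzole, and whether FAB122 alters riluzole levels. The error in the Cmax change runs toward a finding of no interaction, which is what Section 2.1 already expects.

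**Working it through.** The documents give no precision or power figure for the interaction analysis, so there is none to reproduce.

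**1. What the named contrast can estimate**

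| Group | FAB122 present | Riluzole present |
|---|---|---|
| FAB122 + riluzole | yes | yes |
| Riluzole + placebo | no | yes |
| FAB122 without riluzole (not named) | yes | no |

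The first two rows differ only in FAB122, so they inform FAB122's effect on riluzole. Riluzole's effect on FAB122 needs rows one and three, whatever the sample size.

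**2. How many patients are in row three**

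Inputs: about 90% riluzole use (Section 8.3.1), 2:1 allocation (Section 4), and about 90 or about 60 sampled.

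- All 90 on FAB122: 90 × 0.10 = 9 without riluzole, 81 with.
- 90 sampled 2:1: 90 × 2/3 = 60 on FAB122; 60 × 0.10 = 6 without, 54 with.
- 60 sampled 2:1: 60 × 2/3 = 40 on FAB122; 40 × 0.10 = 4 without, 36 with.

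**3. Precision of that comparison**

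The 90% CI for a geometric mean ratio is the estimate multiplied and divided by exp(t × s × √(1/n1 + 1/n2)). Here s = √ln(1 + CV²), and t is the 95th percentile on n1 + n2 − 2 degrees of freedom. Section 2.1 (rationale for dose) gives 28% as the variability of oral FAB122. Treating it as a between-subject CV is an assumption, so 50% is shown as well.

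For 54 vs 6 at CV 28%: s = √ln(1.0784) = 0.275; √(1/54 + 1/6) = 0.430; t = 1.67; exp(1.67 × 0.275 × 0.430) = 1.22.

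| FAB122 with vs without riluzole | CV 28% | CV 50% |
|---|---|---|
| 81 vs 9 | ×/÷ 1.17 | ×/÷ 1.32 |
| 54 vs 6 | ×/÷ 1.22 | ×/÷ 1.40 |
| 36 vs 4 | ×/÷ 1.28 | ×/÷ 1.52 |

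These figures use this trial's data alone, without pooling.

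**4. Change in riluzole Cmax**

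Let R be the true ratio of riluzole Cmax with versus without FAB122, and f the share of the effect (log scale) already present after the first FAB122 dose. In the FAB122 arm, baseline Cmax carries R^f and week 4 carries R, so the observed week 4/baseline ratio is R^(1−f).

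| True R | f = 0 | f = 0.5 | f = 1 |
|---|---|---|---|
| 1.25 | 1.25 | 1.12 | 1.00 |
| 1.50 | 1.50 | 1.22 | 1.00 |

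Subtracting the placebo arm's change does not correct this, because only the FAB122 arm's baseline is affected.

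**5. What is not affected**

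The baseline trough is drawn before the first FAB122 dose, so its change to week 4 captures the effect on trough levels. The between-arm comparison of Cmax levels at week 4 estimates R directly. With about 90 sampled 2:1, that is about 54 riluzole users on FAB122 against 30 × 0.90 = 27 on placebo.

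**The case against.** The strongest reply is that Section 8.3.1 is a summary and the PK analysis plan is the governing document. That plan is not among the documents and may already name the right comparator. Section 8.3.1 itself gives a route to riluzole's effect on FAB122, through co-medication as a population PK covariate. With about 90% of patients on riluzole, it is the obvious co-medication to test. Pooling could add riluzole-free subjects: Section 2.2 lists healthy-volunteer studies of 12, 36 and 60 subjects, although differences in population and dose would need modelling. For riluzole, between-arm Cmax levels are already compared at both visits, and the change is an addition to them. Finally, Section 2.1 expects no interaction, citing separate metabolic pathways and none reported in earlier edaravone trials in which most patients took riluzole.

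Most of this stands, and it rules out two stronger readings. A reader might infer that the plan gives no answer at all on riluzole's effect on FAB122. The documents do not support that, because the covariate test can in principle estimate it and pooling is permitted. A reader might also infer that the whole analysis of FAB122's effect on riluzole fails. It does not, since the week 4 levels and the trough change are sound.

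Three things remain. The protocol sets a two-way aim and names a one-way comparison. The covariate route does not name riluzole and would rest on very few riluzole-free patients. The Cmax change is listed beside valid measures with no warning. A separate plan that follows this wording would inherit all three.

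**Conclusion.** The point holds as a minor one. The only group comparison named cannot inform riluzole's effect on FAB122. That direction depends on an unspecific covariate test with about 4 to 9 riluzole-free FAB122 patients expected, 6 on the most natural reading, unless other studies are pooled. At 54 vs 6 the 90% CI would be about ×/÷ 1.22 at a CV of 28% and ×/÷ 1.40 at 50%.

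The baseline-to-week-4 change in riluzole Cmax understates any effect that begins with the first dose, down to no visible change if the full effect is immediate. This assumes that the first-dose effect is between none and all of the week 4 effect, in the same direction. The documents do not say how large that share would be.

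The counts rest on the plan's own 90% estimate of riluzole use and on how the roughly 90 subjects are read; both CVs are assumptions. No primary, key secondary or safety conclusion depends on this analysis.

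**What to change.** In Protocol Section 8.3.1, carried into the PK analysis plan:

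1. For riluzole's effect on FAB122, name FAB122 with riluzole versus FAB122 without riluzole as the comparison. Estimate it with riluzole use as a prespecified covariate in the population PK model, report a ratio with 90% CI, and state the expected low precision and whether other studies are pooled.
2. For FAB122's effect on riluzole, base the Cmax inference on the between-arm comparison of levels at week 4. Use change from baseline only for the pre-dose trough. Drop the Cmax change, or label it as attenuated because the baseline value follows the first FAB122 dose.
3. Reconcile the description of the roughly 90 sampled subjects as treated with study drug (Sections 1 and 4) with the need for placebo patients among them, and the riluzole sample of about 60 (Section 8.3.1) with about 90 (Section 6.7). State the expected number per arm.

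The cost is wording only, with no extra samples, visits or change to recruitment. It can be done at any time before the PK analysis plan is finalised, which Section 8.3 sets before database closure and code breaking.
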